10.1 Human material

N/A

10.2 Check all the boxes which are applicable to the human material origin:

- Residual material from regular healthcare
- Research (material acquired from a previous study).
Add the reference of the study i.e., MEC-number Erasmus MC.
- Re-use of human material from existing biobank
Describe whether the human material originates from research into the same disease.
- Other, please specify

10.3 Handling and storage of human material

- Anonymous, i.e. the material can never be traced back to an individual subject
- Pseudonymized/Coded
- Identifiable

Describe how human material is handled and stored (i.e. which data management system / data capture system), anonymous / pseudonymized / coded / identifiable, who has access to the human material, how long the human material will be kept, what happens with the data after the research has been completed.

In line with Erasmus MC guidelines, human material will be kept 10 years after it is collected.

10.4 Biobank

In case of new human material collection (biobank), describe how the human material is coded and stored (which registration system, Central Biobank or other location), who has access to the registration system and human material, by whom the key to the code is safeguarded, how long and where human material will be kept, what happens to the human material when the storage period is expired.

Appendix 2 - User Experience USE Questionnaire

		1. Fully disagree	2. Disagree	3. Neutral	4. Agree	5. Fully agree	N/A
	Usefulness						
1	I learned a lot from this simulation about how to perform an ECMO circuit check						
2	The training helped me being more confident in managing ECMO patients						
3	The training helped me remember the steps an ECMO circuit check						
4	After the training, I have enough knowledge to take the lead in an ECMO circuit check						
	Satisfaction						
6	I enjoyed participating in this ECMO simulation						
7	I was satisfied with the quality of this simulation						
8	I would recommend using this simulation to other colleagues						
9	I would prefer VR training additionally to conventional training (shadowing an expert)						
10	I would prefer VR training instead of conventional training (shadowing an expert)						
	Ease of use						

11	The software is easy to use						
12	I learned to use it quickly						
13	The interaction with the software felt intuitive						
14	I can use the software without written instructions						
Immersiveness							
15	I was not distracted during the training						
16	The simulator was realistic						
17	I felt like I was in a real ICU box						
18	I was interested in the progress of the events within the simulation						
19	I felt actively involved in the patient scenario of the training						

Please list and rank, in order of importance from most (1) to least (3), the advantages and disadvantages of training to use an ECMO machine in VR:

Advantages:

- 1.
- 2.
- 3.

Disadvantages:

- 1.

2.

3.

Do you have any additional suggestions or recommendations for enhancing or adding new features to the simulation?

Thank you for participating

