to provide prompts when a student is unsure how to perform a certain step. After completion of the assessment, the VR group will be asked to fill out an objective questionnaire (Appendix 2) based on the standardised USE questionnaire [2] to assess baseline characteristics such as prior experience/training and the usefulness, satisfaction, and ease of use of the VR training modality. Participants from the control group will be given the option to also perform the VR training, and subsequently fill a USE questionnaire about their experience with VR.

Expert Arm

Expert participants will not be randomised, and will all perform the VR-ECMO sim before completing the USE questionnaire. Their data will be used for the face and content validity portion of this study.

Randomisation

Participants in the novice arm will be randomly assigned to either interventional or control group, using <https://www.randomizer.org/> as stated above to generate a group allocation for the participant according to their study ID number.

Blinding

Participants will not be blinded as the differences in the differing nature of the intervention versus control group do not allow for this. Selected study personnel, including those physically facilitating both groups during the intervention phase will not be blinded, as again the study design does not allow for this. Study personnel who facilitate the physical assessment for the novice arm, perform data collection & analysis, including the expert assessor for the video recording, will be blinded.

Burden and risks

We do not foresee any risks or burdens incurred with participation, aside from mild nausea which may occasionally occur during a virtual reality experience. This typically subsides quickly once the head mounted display is removed.

Recruitment and consent

Our study will recruit from two populations for the expert and novice arms of this study. For the former, 10 experts who are experienced perfusionists/intensivists with more than 6 years of experience with ECMO will be included. For the novice arm, the population will include intensive care nurses & cardiothoracic surgery nurses who work at one of the academic hospitals in the Netherlands, with no prior experience with ECMO. We calculated a required sample size of 44 novice participants (22 per group) in order to likely achieve statistically significant results.

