In a related study on the VR-Extracorporeal Simulator (entitled “Virtual Reality Simulation as a Training Tool for Perfusionists in Extra Corporeal Circulation; Establishing Face and Content Validity” currently under peer-review), we showed that experts and novices alike found the simulator to be useful & realistic, and therefore valid for face and content validity. Due to the demonstration of feasibility in a closely related simulator, we aim to demonstrate face and content validity alongside concurrent validity in a single study for the VR-ECMO sim. We hypothesise that VR will enable participants to better learn and retain information through interactive engagement with a virtual reality ECMO simulator versus conventional training.

2. Objective(s)

In this study, the goal is to assess the face, content, and concurrent validity of the VR-ECMO sim by comparing the questionnaire ratings of novices and experts after completing the VR-ECMO sim, and comparing the novice intervention group who completed the VR-ECMO sim versus the control arm (video training) in terms of how well they are able to perform an ECMO circuit check, as rated by an expert.

3. Study type

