4.2. Population (base)

As above; Our study will recruit from two populations for the expert and novice arms of this study. For the former, 10 experts who are experienced perfusionists/intensivists with more than 6 years of experience with ECMO will be included. For the novice arm, the population will include intensive care nurses & cardiothoracic surgery nurses who work at one of the academic hospitals in the Netherlands, with no prior experience with ECMO.

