4.4 Exclusion Criteria

Novices Exclusion criteria

1. Failure to provide informed consent
2. Previous experience with ECMO equipment
3. Any reason that participants may not be able to perform the physical assessment

Experts Exclusion criteria

1. Failure to provide informed consent
2. Less than 6 years' experience with ECMO

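### Expert and novice Usefulness ratings are not comparable: the items ask about the respondent's own gain or knowledge, and the groups do not overlap on ECMO experience

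*Combined protocol and SAP*

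**What the plan says.** Section 2 (Objectives) sets out to assess validity partly by "comparing the questionnaire ratings of novices and experts after completing the VR-ECMO sim". Section 7.2 lists perceived usefulness among the rated domains of the questionnaire, as a secondary endpoint. Section 7.4 applies a t-test, a Mann-Whitney U test or a categorical equivalent to all outcome data at P<.05, and offers ANCOVA if there are confounders, without naming any.

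On who answers, section 4.2 states that "10 experts who are experienced perfusionists/intensivists with more than 6 years of experience with ECMO will be included", and section 4.4 excludes experts with "Less than 6 years' experience with ECMO". The same section excludes novices with "Previous experience with ECMO equipment". According to the Summary (Methods, Expert Arm), experts "will all perform the VR-ECMO sim before completing the USE questionnaire", and "Their data will be used for the face and content validity portion of this study".

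Appendix 2 shows one form, with no separate expert wording. Usefulness item 1 reads "I learned a lot from this simulation about how to perform an ECMO circuit check". Items 2 and 3 ask in the same way about the respondent's confidence and recall of the steps. Item 4 reads "After the training, I have enough knowledge to take the lead in an ECMO circuit check". Every item has an N/A option, and no rule is given for scoring it.

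**The concern.** The simulator is meant to teach people who are new to ECMO. The judgement wanted from experts is whether it would do that. The Usefulness items ask instead what the simulator did for the person filling in the form, or what that person knows afterwards. For someone with more than 6 years of ECMO practice, both answers depend on what they knew beforehand.

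At stake is how a secondary result is read. If experts score Usefulness lower than novices, it may be reported as experts finding the simulator less useful. If the groups agree, that may be reported as support for validity. Neither reading follows when the groups were formed on the characteristic that drives the answers.

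**Working it through.** The documents give no effect size, SD or power for the novice-expert comparison, so there is no planned figure to reproduce. The check has four parts.

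**1. What each Usefulness item measures.**
- Items 1 to 3 (learning, confidence, recall) ask about personal gain. Prior competence leaves less room for gain, so it plausibly lowers expert scores.
- Item 4 asks about a level of knowledge after training. An expert can agree whatever the simulator contributed, so prior competence plausibly raises expert scores.

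**2. Can the direction at domain level be known?** Let d be the expert deficit on each of items 1 to 3 that is due to prior knowledge alone, and u the expert excess on item 4. If the four items were averaged, the expert-minus-novice shift would be (−3d + u)/4. With assumed values on the 5-point scale:
- d = 1, u = 0: (−3 + 0)/4 = −0.75
- d = 1, u = 1: (−3 + 1)/4 = −0.50
- d = 0.5, u = 1.5: (−1.5 + 1.5)/4 = 0.00

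The shift is positive whenever u exceeds 3d. If experts mark N/A on items 1 to 3 and the score averages whatever was answered, only item 4 remains and the score rests on prior knowledge in the upward direction. The documents fix neither d nor u, so they fix neither the sign nor the size. They also do not say that a domain score will be formed. Analysed item by item, the bias is −d on items 1 to 3 and +u on item 4.

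**3. Can ANCOVA separate experience from group?** Let G = 1 for experts and 0 for novices. Appendix 1 (question 5) records ECMO experience in four categories: never, 0-5 years, 5-10 years, more than 10 years.
- Under section 4.4 every novice falls in the first category.
- Under sections 4.2 and 4.4 every expert falls in one of the last two.
- With indicator coding, the indicators for the last two categories add up to G for every participant. Group and experience are then exactly collinear, and no adjusted group effect can be estimated.
- If experience is instead given a numerical score, its slope comes only from differences among the 10 experts. The adjusted contrast then extrapolates that slope down to no experience, where there are no experts.

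**4. How much of the questionnaire is involved?** The items are numbered 1 to 4 and 6 to 19, which makes 4 + 14 = 18. Usefulness is 4 of the 18 items and one of four domains.

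**The case against.** The form is based on a standardised questionnaire, and identical wording in both groups is the natural choice when a comparison is planned. Experts can also express a view on training value elsewhere: item 8 asks about recommending the simulation to colleagues, items 9 and 10 ask about VR in addition to or in place of shadowing an expert, and respondents rank advantages and disadvantages of VR training. Section 1 adds that experts and novices both found a related simulator useful.

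Part of this stands. Those items and the ranking do carry some expert judgement on training value, but indirectly: none asks whether a trainee would learn from the simulator, and none belongs to the Usefulness domain. Identical wording gives comparable scores only if the item means the same to both groups, and a question about personal gain does not. The related study concerned a different simulator, and its instrument is not described, so it is weak evidence either way.

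Three stronger readings are tempting, and the documents do not support them.
- A reader might infer that low expert scores are built in. Item 4 pushes the other way, N/A allows items 1 to 3 to be skipped, and an expert may honestly value the simulator as a refresher.
- A reader might infer that the comparison measures prior knowledge and not the simulator at all. It is confounded; nothing shows that it carries no information on the simulator.
- A reader might attach a probability of a spurious significant result. That would need a size for the prior-knowledge shift and an SD, and the documents give neither, so the figure would only restate its assumptions.

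**Conclusion.** The concern holds as a problem of comparability. Following the plan as written produces a Usefulness contrast in which group and ECMO experience cannot be told apart, and the listed adjustment does not help. Because the direction is open, the bias could create a difference or hide one.

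The scope is limited. The primary outcome and the randomised comparison within the novice arm do not use these ratings across groups. The Satisfaction, Ease of use and Immersiveness comparisons are not affected by this point.

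The conclusion rests on two readings. One is that experts receive Appendix 2 as shown, since no other version appears. The other is that the general testing statement in section 7.4 covers the novice-expert contrast named in section 2, although section 7.4 does not list that contrast itself.

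**What to change.** - **Appendix 2, expert version.** Word items 1 to 4 from the trainee's perspective, or add such items beside the existing ones. Item 1 could become: *Someone new to ECMO would gain a good grasp of the circuit check by using this simulator.*
- **Sections 2 and 7.4.** State that Usefulness is reported separately for experts and novices, without a between-group significance test. The comparisons on the other three domains can stay.
- **N/A answers.** Show the number of N/A answers per item in each group, and do not average a domain score over only the items an expert happened to answer.

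The cost is a second version of an online form with four changed items, and a few sentences in sections 2 and 7.4. Novice and expert Usefulness scores would no longer be compared numerically, but the present wording does not support that comparison anyway. The wording change has to come before experts complete the form. If responses are already in, separate reporting and the N/A counts can still be adopted.

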Appendix 3**Skill Assessment Form**

Step	Completed Correctly		Time to action (min:s)	Comments
	Yes	No		
1. Checking RPM, flow, and pressures				
2. Checking alarm limits for flow, and venous & arterial pressures				
3. Checking for presence of tubing clamps				
4. Checking for colour difference between venous & arterial lines with flashlight				
5. Check cannulation site, and confirm the canula has not moved				
6. Check lines for blood clots, and confirm they are free from kinks or obstructions				
7. Check the oxygenator for fibrinogen strands or blood clots using the flashlight				
8. Check arterial line outflow at the oxygenator for clots				
9. Check FiO2 and gas flow settings				
10. Check that the heparin line is attached to the oxygenator, and confirm the dose on the pump				
11. Check that the backup RPM meter on the ECMO system is functional, and check hand crank is present and operational.				
12. Check the heater cooler temperature settings and check for circulation				

13. Check lab results in the patients electronic health record				
--	--	--	--	--

Additional Comments:
